NCT01167907

WFUHS 00013823

PROTOCOL

Evaluation of Continuous Saphenous Nerve Block to Supplement a Continuous
Sciatic Nerve Block After Ankle Surgery

September 30, 2010

Study Title: Evaluation of a Continuous Saphenous Nerve Block to Supplement a Continuous Sciatic Nerve Block for Postoperative Analgesia Following Ankle Surgery

Principal Investigator: [name] MD

Co-investigator(s): [name] MD

Sponsor or funding source: Department of Anesthesiology at Wake Forest University Baptist Hospital. Pumps for saphenous infusion provided by I-Flow Corporation

Background, Rationale and Context

Orthopedic surgery of the lower extremity is particularly painful, and epidural analgesia or long-acting nerve blocks are commonly employed to reduce post-operative pain. Unilateral peripheral nerve blocks have advantages over epidural analgesia including: limited sympathetic blockade, no interference with bladder or contralateral limb function, and the ability to be discharged to home with a perineural catheter and pump for local anesthetic administration.¹ Patients undergoing ankle arthrodesis or bi/tri-malleolar fracture repairs are expected to have pain primarily in the sciatic nerve distribution, with a lesser component of their pain emanating from the medial side of the lower extremity innervated by the smaller, cutaneous saphenous nerve. At our institution, pain from this surgery is typically managed with a continuous sciatic nerve block maintained for 48-72h, and a single-shot saphenous or femoral nerve block with long-acting local anesthetic to provide 12-24h of saphenous analgesia. In spite of this aggressive regional analgesia approach, many patients still complain of significant pain in the postoperative period, and this study is designed to assess the analgesic effect of a continuous rather than single-shot saphenous block. We hypothesize that patients will have a clinically important reduction of pain score from a longer duration of saphenous nerve block provided by a continuous catheter, which would justify the added complexity of 2 perineural catheters

Ultrasound guidance to facilitate placement of peripheral nerve blocks has been shown to improve the onset time of analgesia, increase success of the block, reduce vascular puncture and increase patient satisfaction.²⁻³ While various ultrasound-guided techniques for single-shot saphenous block have been described in the literature, currently no description of an ultrasound-guided continuous saphenous nerve block is available.⁴⁻⁹ This study will employ an ultrasound-guided technique for continuous saphenous block and describe this technique.

Continuous femoral nerve block is a common practice and could also be used with sciatic block to provide analgesia of the medial ankle instead of a saphenous block. Continuous saphenous block, however, has potential advantages over an inguinal femoral nerve catheter including less bacterial colonization, and preservation of quadriceps motor function.¹⁰ This study will assess the effect of continuous saphenous block on quadriceps function.

Objectives

This study will evaluate the effect of adding a continuous saphenous nerve catheter to a continuous sciatic nerve catheter in patients undergoing ankle surgeries. Specifically, patients undergoing ankle fusions or open reduction and internal fixation of bi- or tri-malleolar fractures will be evaluated. The primary endpoint of this study will be the verbal pain score at rest and with movement at 48h post-nerve blockade. At this point in time the primary saphenous nerve

block will have resolved, and any saphenous analgesia will be due to the infused solution. Secondary endpoints of opioid use, nausea and vomiting, sleep disturbance, and change in quadriceps strength will also be evaluated. Additionally, we will describe an ultrasound guided technique for placement of a continuous saphenous nerve catheter supported by cadaveric dissection.

Methods and Measures

Design

The study will be a randomized, double-blind, placebo-controlled trial. Patients will be recruited and have sciatic and saphenous perineural catheters placed as described below, and initial nerve blocks produced in the usual fashion. Patients will then be randomized to either an active drug (local anesthetic) or a placebo (saline) infusion group at the time of saphenous infusion preparation by Pharmacy personnel.

Setting

All patients in the study will be undergoing non-urgent surgery at Wake Forest University Baptist Medical Center. The interventions will be performed in the regional anesthesia area of the surgery center. Patients will remain in the hospital at least one night, and once discharged, all patients will have daily follow-up by phone with the regional anesthesia acute pain management team.

Subject selection criteria

Patients undergoing non-urgent unilateral ankle arthrodesis or open reduction and internal fixation of bi/tri malleolar fractures will be recruited for the study.

- Inclusion Criteria**

Patients will be eligible for inclusion in the study if they are between the ages of 18-75 and are scheduled to undergo unilateral ankle arthrodesis or open reduction and internal fixation of bi/tri malleolar fractures at Wake Forest University Baptist Medical Center. Patient must give written informed consent for anesthesia including continuous sciatic nerve block and saphenous block for postoperative analgesia prior to recruitment. Patients must be able to comprehend the use and care of the catheters and infusion pump systems both in the hospital, and at once discharged home with verbal and written instructions

- Exclusion Criteria**

Patients will be excluded if they have a contraindication to saphenous or sciatic nerve blockade (including significant coagulation abnormalities), history of opioid addiction, current chronic pain therapy with high-dose opioid (extended release opioids or > 40mg oxycodone equivalents per day), allergy to study medications, or failure to place a sciatic catheter. Failure to achieve successful sciatic analgesia or a successful primary saphenous block will also lead to exclusion.

- Sample Size**

74 patients will be recruited for the study and will be randomized into two groups of $n = 37$ patients each. This sample size provides power = 0.80 to allow reliable detection of group differences of $d = 0.74$ standard deviation units (approximately 1.5 points on a 0 -10 pain scale in our pilot data), assuming two-sided inferences held to the $\alpha =$

0.025 level (see stats section for details on error control). Differences smaller than this magnitude are unlikely to be clinically meaningful.

Interventions and Interactions

Study participants will be asked to report a preoperative baseline pain score (Numeric Pain Scale (0-10)), and have quadriceps strength measured (see below) prior to any sedation being administered. Patients will undergo placement of a continuous subgluteal sciatic nerve catheter, and dosage with 25ml of 0.25% bupivacaine with epinephrine 1:200,000 and clonidine 25 mcg per usual technique after sedation. A perineural catheter will then be placed for primary saphenous nerve block and postoperative saphenous infusion. This continuous saphenous catheter will be placed using ultrasound guidance (Sonosite Turbo™, Bothell, WA) (6-13MHz linear probe). The superficial femoral artery will be identified in short axis at approximately the midpoint or distal third of the femur as the artery lies deep to the sartorius muscle in the adductor canal. Using aseptic technique, an 18 gauge tuohy needle will be inserted in-plane from lateral to the transducer and advanced to a position anteromedial to the artery, between sartorius and vastus medialis muscles. Proper positioning will be confirmed by injection of saline, a 20g multiorifice catheter will be inserted 3-4 cm beyond the needle tip and the catheter will be tunneled and taped up the medial surface of the thigh. The catheter will be test dosed with 1.5% lidocaine with 1:200,000 epinephrine to confirm position and rule out IV injection. The primary saphenous nerve block will be produced by incremental injection through the catheter of 10ml of 0.25% bupivacaine with epinephrine 1:200,000 and clonidine 15 mcg. Successful saphenous block will be defined as loss of sensation to pinprick in the mid, anteromedial leg measured at 15 and 30 minutes post-block. A 3-point scale will be used to define sensory block: 0=full sensation, 1= touch without sharp sensation, 2=absent sensation.

To determine the effect of saphenous block on quadriceps function, patients will have knee extension muscle strength tested pre-block and 30 min post-block using a Hoggan Health microFET 2 MT Digital Handheld Dynamometer. After placement of both the saphenous and sciatic nerve catheters, patients will receive either neuraxial or general anesthesia for surgical anesthesia at the discretion of the attending anesthesiologist medically directing their primary anesthetic technique.

Patients with evidence of sciatic and saphenous nerve block will be randomized to receive a postoperative continuous infusion of either saline (control) or 0.2% ropivacaine by elastomeric infusion pump at 5ml/h started within 6h of catheter placement. The randomization will occur by sealed envelope provided to the OR Pharmacy (block randomization in blocks of 10) and the OR pharmacy will prepare the 300 ml elastomeric pump with active or control solution. The On-Q C-Bloc™(300ml capacity) (I-Flow corporation) pump will be attached to the saphenous catheter in the PACU, or within 6h of primary block; the catheter will infuse for 60 hours.

The patients, physicians, nurses and investigators will be blinded to treatment group.

The sciatic infusion will be managed per usual practice: postoperatively all patients will receive 0.2% ropivacaine through their sciatic nerve catheter at a basal infusion rate of 10ml/h, . The sciatic pump will be an On-Q™ pump per usual practice. All patients will have oral and IV opioids prescribed while hospitalized, and oral opioids prescribed after hospital discharge. In the event of breakthrough pain, patients will be instructed to adjust the sciatic nerve pump, and/or to take oral opioids for the pain.

While patients are hospitalized, opioid administration and pain scores will be recorded by nursing staff on the patient care record. Side effects including nausea, vomiting, or itching will also be recorded. Patients will be seen on a daily basis while in the hospital by the acute pain service, and adjustment of their sciatic infusion performed if indicated. They will be questioned about sleep quality, pain score, opioid side effects, and sensory function in the sciatic and saphenous distributions. This information will be recorded by the acute pain management team. On postoperative day 1, all patients will again have their quadriceps muscle group strength assessed with the hand-held dynamometer, and the catheter sites will be inspected per standard protocol.

Patients will be generally discharged home with peripheral nerve catheters in place on POD #1, after receiving written and verbal instructions in perineural catheter management. These patients will be called at 24 and 48 hours post discharge to determine rest and incident numeric pain scores, opioid usage, sleep quality (as number of awakenings for pain), and the presence of nausea or vomiting. Patients will be given contact numbers and instructions to call with any questions or concerns per usual practice.

Outcome Measure(s)

The primary endpoint of this study will be a reduction of the rest and incident verbal pain scores 48hpost-nerve blockade when the primary saphenous single-shot block is expected to have resolved. Secondary endpoints of reduction of opioid use, nausea and vomiting, sleep disturbance (as number of awakenings), and reduction of quadriceps strength will also be evaluated. Additionally, we will describe an ultrasound guided technique for placement of a continuous saphenous nerve catheter supported by cadaveric dissection.

Analytical Plan

All analyses will be conducted with SAS 9.2 (SAS, Inc., Cary, NC). Prior to conducting the primary analysis, the distributional characteristics of all variables will be considered by examining histograms and descriptive statistics. Where possible, all analyses will be conducted using the general linear model (e.g., t-test), but where necessary nonparametric equivalents will be conducted for pairwise comparisons (e.g., Mann-Whitney U). As a result of random assignment, participant characteristics are expected to be similar, but treatment group characteristics will be compared using descriptive statistics. The primary analysis will consist of a direct comparison between treatment groups at 48 hours using an independent t-test. Because the primary analysis consists of two comparisons (i.e., pain with rest and pain with movement), each comparison will be evaluated at the $\alpha = 0.025$ level (i.e., holding the family to a conservative 5% type-I error rate). Secondary analyses will be conducted using tests appropriate for the level of measurement including t-tests, Mann-Whitney U (ordinal data such as number of awakenings), and χ^2 (categorical data such as presence of nausea). Statistical significance for all secondary comparisons will be interpreted at $p < 0.05$. No interim analyses will be conducted.

Human Subjects Protection

Informed Consent

Written informed consent will be obtained from each subject. Patients scheduled for elective ankle arthrodesis will be seen in the preoperative assessment clinic at North Carolina Baptist Hospital. Following preoperative assessment and consent for peripheral nerve block for analgesia, a research clinician will meet with the patient to discuss participation in the

study. They will be informed of the purpose of the study along with the risks, benefits, and alternatives. Questions will be answered and consent obtained. Patients not seen in our preoperative assessment clinic will be asked to participate in the study on the day of surgery when admitted to the Regional Anesthesia Holding Area. A copy of the signed informed consent will be placed in the patient's medical record. All subjects may decline participation in the study at any time. Informed consent and all necessary study data will be obtained prior to the administration of any sedative medication.

Confidentiality and Privacy

Confidentiality will be protected by collecting only information needed to assess study outcomes, minimizing to the fullest extent possible the collection of any information that could directly identify subjects, and maintaining all study information in a secure manner. To help ensure subject privacy and confidentiality, only a unique study identifier will appear on the data collection form. Any collected patient identifying information corresponding to the unique study identifier will be maintained on a separate master log. The master log will be kept secure, with access limited to designated study personnel. Following data collection subject identifying information will be destroyed at the earliest opportunity, consistent with data validation and study design, producing an anonymous analytical data set. Data access will be limited to study staff. Data and records will be kept locked and secured, with any computer data password protected. No reference to any individual participant will appear in reports, presentations, or publications that may arise from the study.

Data and Safety Monitoring

The principal investigator will be responsible for the overall monitoring of the data and safety of study participants. The principal investigator will be assisted by other members of the study staff.

Reporting of Unanticipated Problems, Adverse Events or Deviations

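### Post-operative opioid use is compared without the pre-operative dose, although eligibility admits both opioid-naive patients and current users; the cost is precision in one secondary endpoint

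*Combined protocol and SAP*

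**What the plan says.** **Who may enter.** Under Exclusion Criteria, the opioid-related exclusions are "history of opioid addiction" and "current chronic pain therapy with high-dose opioid (extended release opioids or > 40mg oxycodone equivalents per day". The dose limit and the extended-release rule both qualify chronic therapy. Nothing addresses short-term use before surgery. Under Subject selection criteria, "Patients undergoing non-urgent unilateral ankle arthrodesis or open reduction and internal fixation of bi/tri malleolar fractures will be recruited for the study".

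**What is measured.** Interventions and Interactions states that "Study participants will be asked to report a preoperative baseline pain score (Numeric Pain Scale (0-10)), and have quadriceps strength measured" before sedation. Pre-operative opioid dose is not named there or elsewhere in the text. After surgery, "While patients are hospitalized, opioid administration and pain scores will be recorded by nursing staff on the patient care record", and after discharge, "These patients will be called at 24 and 48 hours post discharge to determine rest and incident numeric pain scores, opioid usage". The Appendix lists a data collection form, but its content is not shown.

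**How it is analysed.** Outcome Measure(s) states: "Secondary endpoints of reduction of opioid use, nausea and vomiting, sleep disturbance (as number of awakenings), and reduction of quadriceps strength will also be evaluated". The Analytical Plan states: "Secondary analyses will be conducted using tests appropriate for the level of measurement including t-tests, Mann-Whitney U", followed by a chi-square test for categorical data, with significance at 0.05. It names no covariate for any secondary comparison and plans only a descriptive comparison of baseline characteristics. Randomisation uses blocks of 10, with no opioid stratum stated.

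**The concern.** The endpoint is opioid taken after surgery, and nothing in the text separates a continuing habitual dose from new use for surgical pain. A patient who took 30 mg/day before the operation may go on taking some of it whatever is in the saphenous pump. That part of the outcome is fixed before randomisation and has nothing to do with the infusion. It adds between-patient variance, and with 37 per arm the number of users can differ noticeably between arms by chance.

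The dose is a natural covariate, because staff must ask about it to apply the 40 mg limit. The endpoint also helps in reading the primary result: patients with breakthrough pain may take oral opioids or adjust the sciatic pump, so part of any benefit could appear as lower opioid use and not as a lower 48 h pain score. A needlessly noisy comparison weakens that reading.

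**Working it through.** **1. The plan's own figure.** Inputs from Sample Size: d = 0.74, two-sided alpha 0.025, power 0.80, 37 per arm. The normal approximation gives 35 per arm. The noncentral t gives 36.002, rounded up to 37, with power 0.812 at 37. The stated size reproduces. It is driven by the pain score, so nothing below changes it.

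**2. What 37 per arm gives for opioid use.** An unadjusted t-test at two-sided alpha 0.05 and 80% power detects 0.66 SD.

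**3. Variance due to pre-operative dose.** The documents give no opioid distribution or summary measure, so these inputs are assumptions: opioid use in mg/day; a proportion p = 0.2 to 0.4 of patients are users; users' doses are uniform on 5-40 mg/day; the other between-patient SD is 15-25 mg/day; a fraction b of the habitual dose carries over (b = 1 or 0.5).

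- For a user, mean = 22.5 and variance = 35²/12 = 102.1, so the mean square is 102.1 + 22.5² = 608.3.
- Over all patients, variance = 608.3p − (22.5p)².
- p = 0.2: 121.7 − 20.3 = 101.4, SD 10.1. p = 0.4: 243.3 − 81.0 = 162.3, SD 12.7.
- Share of outcome variance = b²V/(b²V + SD₀²), where V is the variance of the pre-operative dose and SD₀ the other SD.
- Full carry-over: low end 101.4/(101.4 + 625) = 0.14; high end 162.3/(162.3 + 225) = 0.42.
- Half carry-over: low end 25.4/(25.4 + 625) = 0.04; high end 40.6/(40.6 + 225) = 0.15.
- With p = 0.1 and full carry-over, V = 55.8 and the share is 0.08 to 0.20.

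Adjustment multiplies the standard error by about √(1 − share). It is therefore 7-24% smaller at full carry-over and 2-8% smaller at half.

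**4. Power after adjustment.** The share equals the squared correlation ρ², so step 3 corresponds to ρ of about 0.37-0.65 at full carry-over and 0.20-0.39 at half. Power is for the effect of 0.66 SD, from a noncentral t on 74 − 3 = 71 df with residual SD multiplied by √(1 − ρ²). The detectable difference is 0.66√(1 − ρ²).

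| ρ | Power at 0.66 SD | Detectable difference (SD) |
|---|---|---|
| 0.2 | 0.81 | 0.65 |
| 0.3 | 0.83 | 0.63 |
| 0.4 | 0.86 | 0.61 |
| 0.5 | 0.895 | 0.57 |
| 0.6 | 0.935 | 0.53 |
| 0.7 | 0.97 | 0.47 |

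At ρ = 0 the lost degree of freedom and the covariate penalty lower power only to 0.794.

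**5. Chance imbalance.** The standard error of the between-arm difference in mean pre-operative dose is SD × √(2/37) = 0.2325 × SD, which is 2.3-3.0 mg/day. At half carry-over, the part that reaches the outcome is half of that. Treating the arms as independent binomials, the chance that they differ by four or more users is 0.17, 0.31, 0.37 and 0.41 at 10%, 20%, 30% and 40% users.

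**6. Validity of the planned test.** In 20,000 simulated trials with no treatment effect and ρ = 0.6, the unadjusted t-test rejected in 4.7%, against a nominal 5%.

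**The case against.** The strongest case is that an unadjusted comparison of a secondary endpoint in a randomised, blinded trial is valid, so a covariate is only a refinement. That stands. A reader might infer that uneven numbers of users would bias the result and so hide or mimic opioid sparing. The documents do not support that: allocation is random, chance imbalance is already within the nominal error rate, and step 6 shows no inflation.

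A reader might also infer that the dose is never recorded and an imbalance could never be checked. This is not established. The text on pre-operative measures does not claim to be complete, the data form is not shown, and screening has to establish the dose in some way. Only its absence from the protocol text and from the planned analysis can be shown.

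It is equally tempting to call opioid use the main supporting evidence. The secondary endpoints are unranked, and adjusting the sciatic pump is a second outlet for breakthrough pain.

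The magnitude is also open to challenge. Every input in step 3 is assumed, and full carry-over is the favourable extreme. It is least plausible for fracture patients, whose pre-operative opioid treats pain that the surgery and the sciatic block then change. Acute users above 40 mg/day are not in the calculation, and the documents do not say that any are expected.

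Finally, the plan prefers the general linear model where possible and lists its secondary tests as non-exhaustive, so a covariate would fit. But none is named, and one chosen after seeing the data would be post hoc.

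**Conclusion.** The point holds as one of efficiency and prespecification. Eligibility allows a mix of naive patients and users, and the planned opioid comparison ignores that known source of variance. The planned test is neither biased nor anti-conservative; it is less precise than it could be, and there is no planned adjustment if users fall unevenly between arms.

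Under the stated assumptions, the gain runs from a standard error about 2% smaller (20% users, half carry-over, other SD 25 mg/day) to about 24% smaller (40% users, full carry-over, other SD 15 mg/day). If few users enrol, or the correlation is 0.2 or less, there is little to gain. Only one secondary endpoint is affected. The 48 h pain comparisons and the 74 patients stand as calculated.

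**What to change.** - Record the pre-operative daily opioid dose in oxycodone equivalents, covering acute and chronic use, on the data form when the 40 mg check is made. If the form already has it, say so in the protocol.
- Report the dose by arm in the baseline table.
- Prespecify the opioid-use comparison as a linear model with arm and pre-operative dose. Name one rank-based alternative for skewed data, adjusted for or stratified by pre-operative use, and fix the rule for choosing it before unblinding.
- Clarify whether the 40 mg limit is meant to cover acute use. No threshold is proposed here.

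The cost is one data item that screening already needs, one row in a table and one degree of freedom. There is no extra visit, procedure or patient.

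### Does using 74 as both the number recruited and the number randomised, with no allowance for missing 48-hour scores, undermine the stated power of 0.80?

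*Combined protocol and SAP*

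**What the plan says.** The Sample Size section says "74 patients will be recruited for the study and will be randomized into two groups of" 37 patients each. It continues "This sample size provides power = 0.80 to allow reliable detection of group differences of" 0.74 standard deviation units, put at about 1.5 points on the 0-10 scale from pilot data, with two-sided alpha 0.025. The Analytical Plan confirms that level for each of the two primary comparisons (pain at rest and pain with movement at 48 hours), both by independent t-test.

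Three other places set the order of events:

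- Design: "Patients will be recruited and have sciatic and saphenous perineural catheters placed as described below". Randomisation comes afterwards.
- Exclusion Criteria: "Failure to achieve successful sciatic analgesia or a successful primary saphenous block will also lead to exclusion". Failure to place a sciatic catheter also excludes.
- Interventions and Interactions: "Patients with evidence of sciatic and saphenous nerve block will be randomized".

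On follow-up, Interventions and Interactions says "Patients will be generally discharged home with peripheral nerve catheters in place on POD #1" and then "These patients will be called at 24 and 48 hours post discharge to determine rest and incident numeric pain scores". The Setting section adds at least one night in hospital and daily telephone contact with the acute pain team after discharge. No block-failure rate, replacement rule, missing-score rate or inflation for loss is given.

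**The concern.** One number serves for two counts that the protocol's own sequence separates. A patient is recruited, has catheters placed and blocks tested, may be excluded, and only then is randomised. The two counts are equal only if no catheter or block fails, and the protocol expects some failures because it writes exclusions for them. A team that stopped at 74 consents would randomise fewer than 74 whenever a block failed.

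The power statement also treats all 37 per arm as analysed. Most patients go home on the first postoperative day, so the 48-hour score will usually be taken by telephone, and some will probably be missed. If the stated 0.80 has little slack, either kind of loss takes power below it and moves the detectable difference above the 1.5 points that the protocol treats as the limit of clinical relevance.

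**Working it through.** **Inputs from the protocol.** Standardised difference d = 0.74, two-sided alpha 0.025, 37 per arm, stated power 0.80 (Sample Size); independent t-test (Analytical Plan). The implied standard deviation is 1.5/0.74 = 2.03 points.

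**Formula.** For arms of n1 and n2, the degrees of freedom are n1 + n2 - 2 and the noncentrality is d / sqrt(1/n1 + 1/n2). Power is the probability that a noncentral t variable falls outside plus or minus the 0.9875 quantile of the central t.

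**Reproducing the stated figure.** With 37 per arm, the noncentrality is 0.74 / sqrt(2/37) = 3.183, the critical value on 72 degrees of freedom is 2.289, and power is 0.812. The stated 0.80 is met.

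**Slack.** Detectable differences are at 80% power and use the implied standard deviation of 2.03.

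| Analysed per arm | Power at d = 0.74 | Detectable d | Detectable points |
|---|---|---|---|
| 37 | 0.812 | 0.730 | 1.48 |
| 36 | 0.800 (0.79998) | 0.740 | 1.50 |
| 35 | 0.787 | 0.751 | 1.52 |
| 33 | 0.760 | 0.774 | 1.57 |
| 30 | 0.713 | 0.814 | 1.65 |

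A 37/35 split gives 0.7996. Power therefore stays at 0.80, to rounding, with 72 of 74 scores.

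**Missing scores (rates assumed; the documents give none).** Of 74 randomised:

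- 5% missing leaves 74 x 0.95 / 2 = 35.2 per arm, power about 0.79.
- 10% leaves 74 x 0.90 / 2 = 33.3, power about 0.76.
- 20% leaves 74 x 0.80 / 2 = 29.6, power about 0.71.

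**Block failures (rates assumed).** If 74 is the number randomised, failures cost no power, only consents: 74/0.95 = 77.9, so 78 (4 more) at 5% failure; 74/0.90 = 82.2, so 83 (9 more) at 10%. If 74 were the number consented, 5% or 10% failure would leave about 35 or 33 per arm, with the powers in the table.

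**Which reading the text supports.** The sentence containing 74 says that those patients "will be randomized into two groups of $n = 37$ patients each", and the power statement that follows refers to that size. Interventions and Interactions randomises only patients with both blocks working. Two groups of 37 randomised patients, all with working blocks, means 74 after the exclusions.

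**Scale of the planning uncertainty.** If the standard deviation were 2.08 rather than 2.03, then d = 1.5/2.08 = 0.72, and power with a full 37 per arm would be 0.788. That is practically the same as losing two patients per arm (0.787).

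**The case for a change.** The strongest case for a change is that the Design section uses recruitment for a step before catheter placement, so it is not simply another word for randomisation. A site that stopped at 74 consents could claim to follow the text. No replacement rule is written, and the protocol itself says that no ultrasound-guided continuous saphenous technique had been described, so a failure rate of zero cannot be assumed. Even with 74 randomised, only about one missing score per arm can be absorbed, and telephone scoring makes some loss foreseeable. One sentence would settle the matter at almost no cost.

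The arithmetic in that case stands, and so does the looseness of the word. What it does not show is a stated figure that the design fails to deliver: 0.80 is correct for the group sizes to which it is attached. The shortfalls rest on rates that the documents do not supply, while the protocol does provide a night in hospital and daily calls, with the primary score due at 48 hours, during the planned 60-hour infusion. Exclusions for failed blocks come before allocation, so in themselves they do not bias the comparison. The clarifying sentence would keep 74, the t-test and the alpha level, so it would restore no power. It could not promise exactly 37 per arm either: randomisation is in blocks of 10, and after seven full blocks (35 in each arm) the last four assignments split evenly with probability (10 x 10)/210 = 0.48. Even the most uneven result, 39 against 35, has power 0.811.

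**Conclusion.** No change follows. Read with the eligibility and randomisation text, 74 is the number randomised, about 37 per arm, and patients whose catheter or block fails are ineligible and do not count towards it. At that size the planned t-test has power 0.812 against a stated 0.80. The real gaps are one loosely used word and an unstated assumption that about 72 of 74 patients give a 48-hour score; a trial team would handle the first sensibly by continuing to enrol until 74 were randomised.

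The possible loss is modest: about one point below 0.80 at an assumed 5% of missing scores and about four points at 10%, with the detectable difference rising from 1.48 to 1.52 or 1.57 points. These figures are illustrative, because no loss rate is given, and they depend on the pilot standard deviation of about 2.03. Whether to inflate for loss or accept slightly lower power is a fair planning choice. The conclusion would be weaker if enrolment had in fact stopped at 74 consents with many block failures, but nothing in the documents indicates that.
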